7.5 Final examinations after the treatment phase (End of Treatment Evaluation visit)

Final examinations should be performed **30±2 days** after last given medication according to protocol.

- Hematological and biochemical laboratory assessment including hemoglobin, thrombocytes, neutrophils, Na^+ , K^+ , Mg^{2+} , Ca^{2+} , ASAT, ALAT, alkaline phosphatase, GGT, bilirubin, urea, creatinine, creatinine-clearance, C-reactive CRP, CEA, CA-19-9
- Assessment of adverse events. Adverse events are recorded according to NCI-CTCAE v.5.0. Serious adverse events have to be reported within 24 h to the Alcedis GmbH (section 9.6)
- If applicable: new tumor therapy
- Survival data
- Females of childbearing potential: urine pregnancy test (β -hCG)

7.6 Examinations during Follow-up Period

The follow-up period will last until the defined end of the study of a maximum of 36 months after last patient recruited.

The following examinations will be performed every 3 months after last treatment administration (if visit at the site is not possible, phone calls count as visit):

- If applicable: new tumor therapy
- Survival data
- Adverse events: Final documentation of outcome of adverse events still ongoing at the End of Treatment Evaluation visit. Documentation of SAEs related to study treatment, until resolution or stabilization.

8 Criteria for Tumor Assessment and Response

8.1 Eligibility for Evaluation

Patients with a measurable disease according to RECISTv1.1 criteria before the start of study treatment are eligible for response evaluation according to RECISTv1.1 criteria (refer to section 8.5 and Appendix 17.2) [44].

Note: The method of tumor response evaluation must not be changed during the course of the study!

8.2 Criteria for Measurable and Non-Measurable Lesions

Measurable lesions are lesions that can be accurately measured in at least one dimension with longest at least 10 mm with CT scan, MRI techniques or spiral CT scan.

Non-measurable lesions are all other lesions, including uni-dimensionally measurable disease and small lesions (lesions without at least one diameter ≥ 10 mm), and any of the following bone lesions, ascites, pleural effusion, cysts and abdominal masses that are not confirmed by imaging techniques.

All measurable lesions up to a maximum of 2 lesions per organ and 5 lesions in total, representative of all involved organs should be identified as target lesions and recorded and measured at baseline. Target lesions should be selected on the basis of their size (in other words the lesions with the longest diameter) and their suitability for accurate repeated measurements. A sum of the longest diameter for all target lesions will be calculated and reported as the baseline sum of the longest diameter. This will be used as reference to objectively characterize the tumor. All other lesions should be identified as non-target lesions and are not measured at baseline but presence should be noted.

8.3 Definition of Measurable Lesion Response Using RECIST Criteria

Version 1.1

Target lesions will be measured in a dimension using the longest diameter is used. The same investigational method must be used throughout.

Complete response (CR): Disappearance of all lesions and appearance of no new lesions.

Partial response (PR): At least a 30% decrease in the sum of the longest diameter of target lesions, taking as reference the baseline sum diameters. No new lesions may occur or individual lesions progress.

Progressive disease (PD): At least a 20% increase in the total of the longest diameters of target lesions, taking as reference the smallest sum on study since the treatment started (this includes the baseline sum if that is the smallest on study) or the appearance of new lesions.

If the marker lesion disappears and the progression of a lesion or the appearance of new lesions is observed elsewhere at the same time, this is also documented as a progressive disease.

Stable disease (SD): Neither a partial nor a complete response in the absence of progression.

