3.3.1 Inclusion Criteria

Patients may be **included** in the study only if they meet **all** the following criteria:

- Histologically confirmed, UICC stage IV adenocarcinoma of the left-sided colon or rectum with metastases (metastatic colorectal cancer), primarily non-resectable, confirmed RAS mutations proven in the primary tumor or metastasis (KRAS and NRAS exon 2, 3, 4)
- Age ≥ 18 years on day of signing informed consent
- No previous chemotherapy for metastatic disease (1 - 2 cycles FOLFIRI or mFOLFIRI are permitted before enrolment until RAS status is determined)

- Patients suitable for chemotherapy administration
- ECOG performance status 0-1
- Consent to liquid biopsy and mutation analysis
- Estimated life expectancy > 3 months
- Presence of at least one measurable reference lesion according to the RECIST 1.1 criteria (chest CT and abdominal CT 4 weeks or less before enrollment)
- Adequate bone marrow function defined as:
 - Leukocytes $3.0 \times 10^9/L$ with neutrophils $1.5 \times 10^9/L$
 - Thrombocytes $100 \times 10^9/L$
 - Hemoglobin 9 g/dL
- Adequate hepatic function defined as:
 - Serum bilirubin $1.5 \times ULN$
 - ALAT and ASAT $2.5 \times ULN$ (in the presence of hepatic metastases, ALAT and ASAT $5 \times ULN$)
- Adequate renal function: Creatinine clearance $\geq 50 \text{ mL/min}$
- Adequate cardiac function defined as
 - Normal ECG and echocardiogram with a left ventricular ejection fraction (LVEF) of 55%
- INR < 1.5 and aPTT < 1.5 $\times ULN$ (patients without anticoagulation). Therapeutic anticoagulation is allowed if INR and aPTT have remained stable within the therapeutic range for at least 2 weeks.
- Time interval of at least 6 months since last administration of any previous neoadjuvant/adjuvant chemotherapy or radiochemotherapy of the primary tumor in curative treatment intention
- Any relevant toxicities of prior treatments must have resolved to grade ≤ 1 according to the CTCAE (version 5), except alopecia
- Women of childbearing potential (WOCBP) should have a negative urine pregnancy test within 72 hours prior to receiving the first dose of study medication.
- Highly effective contraception for both male and female patients throughout the study and for at least 3 months after last dose of study medication administration if the risk of conception exists. Highly effective contraception has to be in line with the definition of the CTFG recommendation (see 17.5)

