8.4 Definition of Non-Measurable Lesion Response Using RECIST Criteria

Version 1.1

Any other lesions, including small lesions (longest diameter < 10 mm or pathological lymph nodes with ≥ 10 to < 15 mm short axis) as well as truly non-measurable lesion are considered non-measurable or non-target lesions. Truly non-measurable lesions include: leptomeningeal disease, ascites, pleural and pericardial effusion, inflammatory breast disease, lymphangitic involvement of skin or lung, abdominal masses / abdominal organomegaly identified by physical exam that is not measurable by reproducible imaging techniques.

Evaluation of non-target lesions:

Complete Response (CR): Disappearance of all non-target lesions

Incomplete Response/Stable Disease (SD): Persistence of one or more non-target lesion(s)

Progressive Disease (PD): Appearance of one or more new lesions and/or unequivocal progression of existing non-target lesions

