10.1.2 Secondary Variables

- OS, defined as time from date of randomization until death from any cause; OS should be censored, in patients without an OS event, on the last date they were known to be alive.
- TFTS, is defined as time from date of randomization to failure of treatment strategy defined as treatment discontinuation for any reason, including disease progression, withdrawal of consent, treatment toxicity, patient preference, loss to follow up or death from any cause.
- PFS rate 1 year after date of randomization, derived by Kaplan-Meier method (defined as the estimated rate of patients with progression or death from any cause 1 year after date of randomization)
- Depth of response (DpR) in terms of reduction of tumor mass in experimental and control arms, defined as the percentage of tumor shrinkage, based on longest diameters of all target lesions or reconstructed volume, observed at the lowest point (nadir) compared to baseline. The time for DpR assessment varies between patients relating to the individual achievement of maximal tumor shrinkage, which typically occurs 4–6 months after the start of 1st-line therapy. DpR varies between 100% (= all target tumor lesions have disappeared) and 0% (=no change in tumor size) and has a negative value in cases of increased tumor volume.
- Percentage of patients with metastasis resections, defined as percentage of patients with complete resection of primary tumor and metastases (R0-resection), at any time after the start of 1st line therapy until the end of the treatment strategy.
- ORR, defined as the proportion of randomized patients with CR or PR as best response since start of 1st line therapy.
- Safety, defined as all SAEs regardless of causality, and non-serious adverse events according to CTCAE Version 5.0 criteria, that are definitely, probably, or possibly related to the administration of any study treatment, or that cause permanent discontinuation of treatment, recorded from the date of signature of Informed Consent.

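### The written progression rule for target lesions has no minimum absolute increase, so from nadir sums of 5–20 mm a rise of 1–4 mm counts as a PFS event

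*Protocol*

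**What the plan says.** Protocol 8.3, headed as RECIST version 1.1, calls target-lesion progression on "At least a 20% increase in the total of the longest diameters of target lesions, taking as reference the smallest sum on study". The rest of the sentence widens the reference and adds one other route to progression: "this includes the baseline sum if that is the smallest on study) or the appearance of new lesions". No absolute increase is required. None is added in 8.4, in the response table in 8.5 or in Appendix 17.2, which covers only measurability and baseline rules.

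The primary variable (Protocol 10.1.1; SAP 4.12) counts progression according to RECIST v1.1, or death, as the event. SAP Listing 24 reports the progression date and PFS for each patient, Figure 2 plots PFS, and Listing 23.1 records the sum of lesion sizes in millimetres at each assessment. The SAP does not describe deriving progression from those sums.

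Small sums can occur. Entry requires "Presence of at least one measurable reference lesion according to the RECIST 1.1 criteria", and a lesion is measurable if it is "longest at least 10 mm with CT scan, MRI techniques or spiral CT scan". Section 10.1.2 allows shrinkage up to complete disappearance: "DpR varies between 100% (= all target tumor lesions have disappeared) and 0% (=no change in tumor size".

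**The concern.** A purely relative threshold shrinks with the tumour. The smaller the nadir, the fewer millimetres separate stable disease from progression, until the gap is about the size of ordinary reading variation. A patient whose disease has not changed can then be given a progression date, and that date is the primary endpoint. The patients exposed are those with the smallest sums, including the deepest responders.

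The trial is open-label and the documents describe no central reading of scans, so nothing in the plan would catch a marginal call. Scans recur every 8 weeks in the first year, so each patient at a small nadir meets the threshold repeatedly.

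**Working it through.** **The plan's own figure.** The hazard ratio is ln 0.5 / ln 0.3 = 0.5757, as stated in Protocol 10.4. Freedman's formula gives (1.960 + 0.842)² × (1.5757 / 0.4243)² = 108.2 events, about 1% above the stated 107. With exponential PFS, 58 patients per arm, 18 months of uniform accrual, 0.25% monthly drop-out and 52 months in total, the expected events are 55.8 + 51.2 = 107.0. The plan's figure reproduces, and none of its inputs involves the progression threshold.

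**Inputs for this point.** The relative threshold is 20% of the smallest sum (8.3). The smallest measurable lesion is 10 mm (8.2) and one is enough (3.3.1). Partial response is "At least a 30% decrease in the sum of the longest diameter of target lesions, taking as reference the baseline sum diameters".

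**Rise that counts as progression = 0.20 × nadir sum.**
- 5 mm: 1.0 mm
- 7 mm (a 10 mm lesion at the 30% response limit): 1.4 mm
- 10 mm: 2.0 mm
- 15 mm: 3.0 mm
- 20 mm: 4.0 mm
- 25 mm: 5.0 mm
- 50 mm: 10.0 mm

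So 1–4 mm corresponds to nadir sums of 5–20 mm.

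**How small a sum this requires.** Reaching 20 mm takes 33% shrinkage from 30 mm, 60% from 50 mm and 80% from 100 mm.

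**Effect of a minimum.** With a minimum of m mm the threshold is max(0.20 × S, m), where S is the nadir sum. It differs from the written rule only when S < 5m: below 15 mm for m = 3, below 20 mm for m = 4 and below 25 mm for m = 5. The documents give no value of m, so all three are assumptions.

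**Chance of false progression at one later scan.** Assume no true change and a normal reading error with standard deviation s for the sum. The difference of two readings has standard deviation s√2, and the chance is 1 − Φ(threshold / (s√2)). For S = 15 and s = 1.5, s√2 = 2.121. The written rule gives 1 − Φ(3 / 2.121) = 7.9%, and a 5 mm minimum gives 1 − Φ(5 / 2.121) = 0.9%.

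| Nadir sum | s (assumed) | Written rule | With 5 mm minimum |
|---|---|---|---|
| 15 mm | 1.5 mm | 7.9% | 0.9% |
| 15 mm | 2.5 mm | 19.8% | 7.9% |
| 20 mm | 1.5 mm | 3.0% | 0.9% |
| 20 mm | 2.5 mm | 12.9% | 7.9% |
| 25 mm or more | any | same | same |

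A 4 mm minimum would give 3.0–12.9% at 15 mm and leave 20 mm unchanged. A 3 mm minimum would change neither. At a 10 mm nadir with s of 1–2 mm, the written rule gives 7.9–24% and a 5 mm minimum 0.02–3.9%.

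The calculation ignores that the nadir is the lowest of several noisy readings, which would raise the chance under either rule.

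**The case against.** **RECIST v1.1 is invoked by name.** Section 8.1 cites its source, and the primary objective and the PFS definition refer to it, so assessors may apply the source rather than the 8.3 summary. This is fair, and it is why one cannot say that every 1–4 mm rise would in practice have been called. It does not cure the text: 8.3 is the definition printed under that heading, and the places to which 8.1 sends the reader (8.5 and 17.2) add no minimum. The source is not among the documents, so this review cannot say what it requires, only that the two must agree.

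**Small sums may be rare.** One 10 mm lesion is the eligibility floor, not the typical case. Patients have non-resectable stage IV disease, and up to five of the largest lesions are summed. This stands. The documents show that small nadirs are possible, not that they are expected.

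**The 10 mm limit concerns lesion classification.** Section 8.2 describes a measurable lesion as one "accurately measured in at least one dimension with longest at least 10 mm", and 8.4 classes as non-measurable "Any other lesions, including small lesions (longest diameter < 10 mm". These limits sort lesions; they do not state the precision of a follow-up sum. This also stands, so the reading SDs rest on assumption alone. One SD is used whatever the number of lesions in the sum.

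**Bias against Arm A is not shown.** A reader might infer that the rule biases the primary comparison toward no effect because cetuximab deepens response. The protocol expects longer PFS in Arm A (2.6), but that is not a statement about depth of response. The reference sum also includes shrinkage during FOLFIRI before randomization, which is common to both arms. If responses are deeper in Arm A, false events would fall more often there; the documents do not allow that to be quantified.

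**Treatment is not stopped automatically.** A reader might infer that reading error would end treatment. Section 5.4.1 leaves discontinuation after progression to the treating physician.

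**Conclusion.** The point holds as a defect in the written endpoint definition. Followed literally, 8.3 turns a 1–4 mm reading difference into a PFS event when the nadir sum is 5–20 mm. That range is arithmetic from the protocol's own figures. The false-progression probabilities are illustrations that rest on the assumed reading SDs, no true change and, for the comparison, the assumed 5 mm minimum. The number of patients affected cannot be stated.

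The practical reach is limited. Enrolment closed at seven patients (SAP 4.2), significance levels are not applicable (SAP 4.19), and the SAP plans listings and Kaplan-Meier plots. What can be wrong is an individual PFS date in Listing 24 and a step in Figure 2, which is visible with so few patients. No significance test is affected, and the 107-event calculation does not change. This is a correction that should be made because it is cheap, not a flaw that invalidates the trial.

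**What to change.** Reconcile the progression wording in Protocol 8.3 and Appendix 17.2 with the RECIST v1.1 source cited in 8.1, and state there the absolute minimum increase that applies alongside the 20% rule. The 5 mm used above is an assumption for illustration.

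For the PFS endpoint, have the SAP derive the target-lesion progression date with that minimum from the sum of sizes in Listing 23.1, keeping new lesions and non-target progression as separate routes. Use it for Listing 24 and Figure 2, and flag every progression date that would differ without the minimum. The change concerns endpoint dating only; treatment decisions after progression stay as the protocol states.

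The cost is one clause in the protocol, one derivation rule in the SAP and a check on data already recorded. The downside is that true progression from a very small nadir may be dated one scan later.

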8.4 Definition of Non-Measurable Lesion Response Using RECIST Criteria

Version 1.1

Any other lesions, including small lesions (longest diameter < 10 mm or pathological lymph nodes with ≥ 10 to < 15 mm short axis) as well as truly non-measurable lesion are considered non-measurable or non-target lesions. Truly non-measurable lesions include: leptomeningeal disease, ascites, pleural and pericardial effusion, inflammatory breast disease, lymphangitic involvement of skin or lung, abdominal masses / abdominal organomegaly identified by physical exam that is not measurable by reproducible imaging techniques.

Evaluation of non-target lesions:

Complete Response (CR): Disappearance of all non-target lesions

Incomplete Response/Stable Disease (SD): Persistence of one or more non-target lesion(s)

Progressive Disease (PD): Appearance of one or more new lesions and/or unequivocal progression of existing non-target lesions

8.5 Best Overall Response According to RECIST Criteria

Target lesions	Non-target lesions	New lesions	Overall response
CR	CR	No	CR
CR	SD	No	PR
PR	SD	No	PR
SD	SD	No	SD
PD	any	Yes or No	PD
any	PD	Yes or No	PD
any	any	Yes	PD

9 Assessment of Safety

Toxicities will be defined according to the Common Terminology Criteria for Adverse Events (CTCAE) version 5.0 (Appendix 17.3).

The investigator is responsible for documenting all adverse events that occur during the study. Adverse events have to be reported after informed consent until 30 days after last dose of study treatment. Then only adverse events which are causally related to study treatment have to be reported.

9.1 Adverse Events

Adverse events (AEs) are any untoward medical occurrence in a patient or clinical investigation subject administered a pharmaceutical product and which does not necessarily have a causal relationship with this treatment. An adverse event (AE) can therefore be any unfavourable and unintended sign (including an abnormal laboratory finding), symptom, or disease temporally associated with the use of a medicinal (investigational) product, whether or not related to the medicinal (investigational) product (see the ICH Guideline for Clinical Safety Data Management: Definitions and Standards for Expedited Reporting).

This also includes deterioration in pre-existing diseases or events, diseases that occur in the intervening period, changes of medication or a significant deterioration in the disease studied. Expected daily variations in the disease under study that do not represent a clinically significant deterioration should not be considered an AE.

Unexpected adverse event is defined as:

an experience not previously reported (in nature, severity or incidence) in the current Investigator's Brochure, SmPC, the protocol or elsewhere (ICH E.G. (R1) guideline, July 2002).

A **non-serious adverse event** is an AE not classified as serious.

Laboratory test abnormalities

All laboratory test results captured as part of the study should be recorded following institutional procedures. Test results that constitute SAEs should be documented and reported to Alcedis GmbH as such.

The following laboratory abnormalities should be documented and reported appropriately:

- any laboratory test result that is clinically significant or meets the definition of an SAE
- any laboratory abnormality that required the participant to have study drug discontinued or interrupted
- any laboratory abnormality that required the patient to receive specific corrective therapy.

It is expected that wherever possible, the clinical rather than laboratory term would be used by the reporting investigator (e.g., anemia versus low hemoglobin value).

9.2 Serious Adverse Events

A serious adverse event (SAE) is any event that

- Results in death
- Results in a life-threatening condition (defined as an event in which the participant was at risk of death at the time of the event; it does not refer to an event which hypothetically might have caused death if it were more severe)
- Results in persistent or significant disability/incapacity (defined as impairment of the ability of the patient to go about his/her daily life normally)
- Results in congenital abnormalities or birth defects
- Requires hospitalization or prolongation of existing hospitalization
- Any important medical event that may not result in death, be life-threatening, or require hospitalization may be considered serious when, based upon appropriate medical judgment, it may jeopardize the patient or subject and may require medical or surgical intervention to prevent one of the outcomes listed above.

Although pregnancy is not always serious by regulatory definition, however, these events must be reported within the SAEs timeline.

EXCEPTIONS:

Within this study, the following serious events are not considered SAEs will be excluded from compulsory notification.

- A visit to the emergency room or other hospital department < 24 hours, that does not result in admission (unless considered an important medical or life-threatening event)
- Elective surgery, planned prior to signing consent
- Hospitalization associated with therapeutic measures exclusively (administration of the trial substances, blood transfusions, elective procedures and surgery for tumor removal).
- Overnight hospitalizations occurring exclusively for logistical reasons (e.g., no transportation available for the patient to return home on the same day).
- Progression of the underlying disease only, even if life-threatening or results in death.

9.3 Follow-Up Examination in the Case of Adverse Events

The investigator should follow up patients with AEs until the event regresses or the condition has stabilized or until end of therapy (for AEs) and until end of therapy plus 30 days (for SAEs). After the safety observation period, the investigator shall report to Alcedis GmbH only serious adverse events that are related to the study medication.

